1.0 Objectives / Specific Aims

Patient-centered oncology care guided by patient-reported outcomes (PROs) is highly prioritized by the American Cancer Society (ACS). Routine use of PROs in cancer care is associated with improved processes of care and patient outcomes. Body image disturbance is a multidimensional construct characterized by a displeasing self-perceived change in appearance and/or function associated with psychosocial distress; it can be assessed using PROs. **Body image disturbance (BID) is prevalent**, occurring in more than 75% of head and neck cancer (HNC) patients. It is also a source of **significant morbidity** causing stigmatization, social isolation, and decreased quality of life (QOL). Unfortunately, there is a paucity of data on the topic. Although managing body image concerns is a **key component of HNC survivorship care** according to the ACS, **effective treatments for BID in HNC patients remain unknown**. HNC often requires multimodality therapy including surgery followed by radiation with/without chemotherapy. While many patients consider the toxicity and side effects of chemotherapy prior to treatment, the life-altering morbidity from surgery related to disfigurement, difficulty swallowing, and challenges speaking has not been addressed. As a result, we are unable to deliver optimal patient-centered cancer care. Therefore, the overarching focus of this translational program of research is to develop and implement effective, therapeutic interventions for BID. Cognitive behavioral therapy (CBT) is a promising approach to treat BID. However, the effects of CBT on BID in surgically-treated HNC have not been examined. Therefore, the study will evaluate whether a time-limited CBT intervention in the post-treatment time period can address BID in patients with surgically-treated HNC, thereby improving BID and QOL.

Specific Aim: Evaluate the effects of cognitive behavioral therapy on body image disturbance in patients with surgically-treated head and neck cancer.

[figure not shown]
Data from our ongoing research show 85.7% of surgically-treated HNC patients have BID at 1 month postoperatively. 69.6% of these patients report being “likely” or “highly likely” to seek treatment for BID if it were available. Effective treatments for HNC patients with BID remain unknown; however prior work has demonstrated that CBT is an effective intervention for a multitude of psychological and behavioral concerns. Therefore, we will complete a single-arm, phase II pilot study of time-limited CBT on BID in patients with surgically-treated HNC. Reliable, validated PRO measures of BID will be collected before, 1 month and 3 months after the CBT intervention to provide preliminary data on the effectiveness of CBT for BID in patients with surgically-treated HNC, addressing this critical knowledge gap. We expect that time-limited CBT implemented in the post-treatment period will decrease BID and improve QOL in affected patients.

2.0 Background

2.a Head and Neck Cancer (HNC) is common, has high mortality, and significant morbidity. HNC is the 6th most common cancer worldwide with 630,000 new diagnoses annually and 350,000 deaths/year¹. 60,000 patients are diagnosed with HNC annually in the US, causing 12,000 deaths/year². Because HNC arises in cosmetically and functionally critical areas such as the face, tongue, and larynx, there is substantial life-altering morbidity from HNC and its treatment related to disfigurement, difficulty chewing and swallowing, altered smiling, and challenges speaking, with resultant functional and psychosocial impairment and decreased quality of life³⁻⁷.

2.b. Body Image Disturbance (BID) in HNC is due to Disfigurement and/or Dysfunction from HNC and its Treatment. BID is a multidimensional construct characterized by a displeasing self-perceived change in appearance and/or function associated with psychosocial distress⁸. Several conceptual frameworks exist for understanding BID^{6,8-13}. One proposes that BID results from both dysfunction and disfigurement with moderating patient, social, and environmental factors influencing the extent of BID over time⁶. Another construct explains body image using image evaluation, the degree to which one is satisfied with one's appearance, and image investment, the value attached to appearance and physical attributes¹⁴ (**Figure 1**).

Fig 1. Conceptual Model of Body Image Disturbance

2.c. BID is Common in HNC Patients and has Numerous Deleterious Consequences. Leading organizations such as the Institute of Medicine and Commission on Cancer emphasize the importance of distress in oncology patients^{19,20}. BID is a major cause of psychosocial distress for oncology patients¹². HNC patients are an extremely high risk group, as more than 75% of patients express body image concerns^{21,22}. The high prevalence of BID in HNC is attributed to cancer- and treatment-related changes in a highly visible, socially significant part of the body that is integral to self-conception, communication, and interpersonal relationships^{6,7,11}. BID results in critical psychosocial impairments, adversely affecting quality of life (QOL) (**Table 1**)^{6,11}. It also represents a large unmet need²³, as 69% of HNC patients are dissatisfied with information from clinicians on body image²⁴.

Increased social isolation ¹⁵	Increased stigmatization ⁶
Altered intimacy and relationships ¹⁶	Increased depression ⁷
Decreased return to workplace ^{17,18}	Increased distress ⁶

2.d. Patient-Reported Outcome Measures are Critical to Study Body Image in HNC. A Patient-Reported Outcome (PRO) is a report of a patient's health condition originating directly from the patient²⁵; they are assessed using validated instruments. PROs are essential to the study of BID due to its subjective, patient-centric nature. PROs are critical for oncology trials²⁶⁻²⁹, quality improvement initiatives³⁰, and comparative effectiveness research³¹⁻³⁴. Patient-centered oncology care with a focus on PROs is prioritized by major funding, policy making, and regulatory entities, including the American Cancer Society (ACS) and the National Cancer Institute^{28,32,35}. Incorporation of PROs into routine cancer care is associated with beneficial outcomes including survival³⁶⁻³⁸. **PROs are essential to the study of BID; oncology care is enhanced when guided by PROs.**

2.e. Cognitive Behavioral Therapy is an Effective Intervention to Address Body Image Disorders. Cognitive behavioral therapy (CBT) refers to a group of interventions based on the premise that maladaptive beliefs about self and the world contribute to psychological distress and problematic behaviors³⁹. Therapeutic strategies that target these maladaptive cognitions by teaching patients to identify and replace these thoughts with more reality-based ones result in symptom reduction and functional improvement³⁹. Extensive literature supports CBT protocols to address conditions such as substance abuse, depression, and anxiety³⁹. Numerous studies show that stand-alone CBT is effective in treating BID, producing durable treatment gains^{40,41}.

Innovation:

2.f. Intervention Strategy: Cognitive Behavioral Therapy (CBT) is a Novel Intervention to Treat BID in Patients with HNC. CBT for BID produces decreases in body dissatisfaction and distress and improvements in self-esteem⁴¹. However, stand-alone CBT for BID has been tested primarily in breast cancer^{12,42} or non-oncologic populations⁴⁰. Qualitatively, HNC-related BID differs from other types of BID due to the functional changes following HNC treatment⁸. Data are lacking on effective interventions to treat BID in HNC patients and CBT offers a promising approach. **This study offers a novel intervention to treat BID in HNC patients, filling a knowledge gap and addressing a critical psychosocial need, thereby improving HNC care.**

[figure not shown]
2.g. Methods: Direct-to-Consumer (DTC) Telemedicine is an Innovative Approach to Delivering Psychosocial Services to Rural HNC Patients in South Carolina. We expect that delivery of 5, weekly CBT sessions to HNC patients with BID (**3.b**; CBT intervention) may prove challenging for some patients, as 76.4% of them travel >50 miles to MUSC for their HNC surgery (unpublished data). To overcome this possible travel-related barrier, we propose the innovative solution of offering the option of a home-based, DTC telehealth platform to deliver CBT to those who cannot travel (**3.b**; telehealth details). Telehealth provides effective behavioral health interventions⁴³ and is associated with decreased travel burden⁴⁴ and increased access to oncology care in rural areas⁴⁵. There is evidence to support that telemedicine CBT is not inferior to face-to-face CBT⁴⁶⁻⁴⁸. Our telehealth services will be supported by the Center for Telehealth at MUSC, one of only two centers in the United States designated a Telehealth Center of Excellence⁴⁹. **We will employ existing expertise in telehealth at MUSC to facilitate delivery of CBT to HNC patients with BID who cannot travel for CBT.**

Preliminary Studies:

2.h. Candidate's Academic Background. This proposal builds upon the publications, grants, and clinical expertise of the study team headed by [name]. He is a junior surgeon-scientist with a clinical and translational research program focused on improving patient-centered HNC care. He joined the faculty at MUSC in the Department of Otolaryngology-Head & Neck Surgery as a surgeon-scientist in 2017 and is also an Associate Research member of the Hollings Cancer Center (HCC) Cancer Control Program. During six years of residency and fellowship, he published 32 manuscripts (21 as first author) in the core otolaryngology and oncology journals, gave 5 national presentations, and received 3 internal grants as principal investigator (PI) for HNC projects. During residency, he was the PI of a funded, investigator-initiated single-arm phase II study in which he developed and implemented a perioperative education intervention for patients undergoing total laryngectomy and showed that the intervention has the potential to decrease unplanned readmissions⁵⁰. He also has relevant national leadership roles, serving on the American Head and Neck Society (AHNS) Survivorship, Reconstruction, and Quality Committees. **[name] has a track record of scholarly activity in patient-centered translational HNC research. This proposal utilizes his research and clinical expertise in HNC quality and reconstruction, leverages the world class resources at MUSC and HCC, and facilitates his progression into an independent investigator advancing patient-centered HNC care.**

2.i Candidate's Prior Work: Prospective Cohort Study of BID in Patients with Surgically-Managed HNC. Our ongoing research utilizes a novel prospective cohort study design to characterize the short-term course of BID in patients with surgically-treated HNC using the Body Image Scale (BIS), a validated, 10-item PRO measure of BID in oncology patients¹³. Our preliminary data for patients with at least 1 month of postoperative follow-up ($n=28$) demonstrate that BID is both common and increases over time. 67.9% of patients reported BID preoperatively; this increased to 85.7% at 1 month after surgery (**Figure 2**). In the subset of patients who reported no BID preoperatively, 55.9% developed BID at 1 month after surgery.

Figure 2. Frequency of Body Image Disturbance

We also found that pre-operative PRO measures of depression, social satisfaction, social isolation, shame/stigma were associated with a BIS of ≥ 5 at 1 month after surgery (all $p < 0.05$); but that demographic and oncologic characteristics were not predictive (see **Table 2**).

Table 1: Univariate associations of demographic, oncologic, and psychosocial variables with 1 month post-operative body image scale scores.

Variable		1 month post op BIS < 5 (n = 14)	1 month post op BIS ≥ 5 (n = 14)	p-value [†]
Variable		Summary measure*	Summary measure*	p-value [†]
Age	median (IQR)	62.5 (53 – 71)	55 (42 – 59)	0.10
Race	White	11 (79)	11 (79)	>0.99
	Non-white	3 (21)	3 (21)	
Sex	Male	12 (86)	8 (57)	0.21
	Female	2 (14)	6 (43)	
Marital status	Married	9 (64)	5 (36)	0.13
	Non-Married	5 (36)	9 (64)	
BMI	median (IQR)	25.5 (21.0 – 26.9)	27.0 (21.2 – 35.7)	0.47
Reconstruction	Free Flap	4 (29)	5 (36)	>0.99
	Non-Free Flap	10 (71)	9 (64)	
Prior Head & Neck Cancer	No	7 (50)	6 (43)	>0.99
	Yes	7 (50)	8 (57)	
Pre-treatment PRO	Anxiety	9 (5 – 11)	10.5 (9 – 13)	0.13
	Depression	4 (4 – 6)	8 (6 – 13)	0.03
	Social Satisfaction	20 (16 – 20)	13.5 (9 – 16)	0.0035
	Social Isolation	4 (4 – 4)	7 (4 – 12)	0.0041
	Shame and Stigma	11 (5 – 14)	19.5 (17 – 34)	0.0091

Abbreviations: BIS = Body Image Scale; IQR = inter-quartile range; PRO = Patient-reported outcome

*Summary measures are median (IQR) for continuous variables, and frequencies (percent) for categorical variables.

†Wilcoxon rank-sum test for continuous variables; Fisher's exact test for categorical variables

HNC patients also expressed an interest in seeking treatment for their BID if it were available. Prior to surgery, 63.9% of patients reported that they were 'somewhat likely' or 'highly likely' to obtain treatment for their BID if it were available; this number increased to 69.6% at 1 month after surgery. **Our ongoing research provides novel preliminary data about risk factors for BID following HNC surgery, shows that BID increases in frequency after surgery, and confirms that it represents an area of unmet cancer care need.**

3.0 Intervention to be studied

3.a. Development of a CBT Module for HNC Patients with BID. Although extensive literature exists for implementation of disorder-specific CBT³⁹, no specific CBT modules for HNC patients with BID exist. Therefore a critical initial step is to establish a disorder-specific CBT intervention for HNC patients with BID. In conjunction with [name], [name] will develop a 5-week, CBT module for HNC patients with BID using CBT core components (i.e. psychoeducation, self-monitoring, and cognitive restructuring). The intervention will be informed by existing CBT from other body image disorder realms^{40,41}. The intervention

will contain population-specific components including identifying and modifying maladaptive beliefs about disfigurement and functional changes following surgery. It will address the multidimensional nature of BID in HNC patients⁶ and will seek to reduce avoidance behaviors, improve social support, and enhance adaptive stress management skills.

3.b. CBT Intervention and Implementation. At the 1-month post-HNC treatment time point, patients with BID as determined by BIS score ≥ 5 will undergo time-limited CBT consisting of 5 weekly sessions. Each session will be guided by the HNC BID module that we develop (**C.2.b.4**) but customized to each patient's specific concerns⁴⁰. Each session will last ~60 minutes and be conducted one-one with [name], who will administer the CBT as part of clinical psycho-oncology care at HCC. Patients will complete questionnaires prior to CBT and 1 and 3 months after CBT (**Figure 4**). We considered alternate dose schedules of CBT but chose a 5-week schedule because evidence suggests that brief (e.g. 5-week) CBT reduces anxiety and depression and improves QOL in cancer patients⁵⁸. To overcome the expected travel distance-related barrier to receipt of CBT (**2.8**), we will offer the option of home-based, telemedicine CBT through an existing MUSC program⁵⁹. This will consist of one CBT session at HCC followed by iPad-based, tele-CBT for the next 4 sessions. Patients will receive the iPad and brief training session from MUSC Center for Telehealth staff at the in-person CBT session. They will take the iPads home, use them for the next 4 tele-CBT sessions, and mail them back to MUSC at the study conclusion. This strategy, which has been successfully piloted at MUSC⁵⁹, addresses the fact that most telehealth usability issues, especially in geriatric patients, occur during initiation⁴³. Introducing a second method of delivering CBT (i.e. telehealth CBT vs in-person CBT) will complicate analysis of the effectiveness of CBT by increasing study heterogeneity. However, we expect that this analytic challenge will be outweighed by the increased enrollment related to telehealth CBT for those who cannot travel to HCC for weekly CBT.

4.0 Study Endpoints

4.a. Primary Endpoint

4.a.1. Body Image Disturbance. The primary outcome measure will be BID as measured by the Body Image Scale (BIS). The BIS has been validated in oncology patients¹³ and is the most widely used scale for BID in oncology⁶. It is a 10-item measure that is scored on a 4-point Likert scale; higher scores indicate greater body image dissatisfaction. It addresses the affective, cognitive, and emotional aspects of body image⁶⁰.

4.b. Secondary Endpoints.

4.b.1. Body Image Investment. Body image investment (i.e. the importance and influence of appearance) will be measured using the Appearance Schemas Inventory-Revised (ASI-R)⁶¹. This 20-item measure is scored using a 5-point Likert scale with greater scores indicating greater body image investment.

4.b.2. Body Image Coping. The Body Image Coping Strategies Inventory (BICSI) is a validated measure used to assess cognitive and behavioral responses to manage threats to body image⁶².

4.b.3. HNC QOL. We will employ the EORTC QLCC30/H&N35 module to evaluate QOL⁶³.

4.c. Exploratory Endpoints for Mediator Analysis. These following endpoints will be used to determine whether changes in BID over time as measured by the BIS are mediated through these variables. They will also be incorporated into a regression analysis to identify characteristics of sub-populations of patients who benefit from CBT for BID.

4.c.1. Shame and Stigma. The Shame and Stigma Scale is a 20-item, validated tool that measures shame with appearance, stigma, regret, and social/speech concerns in patients with HNC⁶⁴.

4.c.2. Depression and Anxiety. Patient-Reported Outcomes Measure Information System (PROMIS) measures of depression and anxiety will be employed. PROMIS measures are validated questionnaire developed by the NIH for evaluating health-related quality of life⁶⁵.

4.c.3. Social Roles and Isolation. Social roles and isolation will be assessed by PROMIS measures⁶⁵.

4.c.4. Head and Neck Performance Status and Function. Performance Status Scale for Head & Neck Cancer, which assesses performance in domains of eating, speech, and diet⁶⁶.

4.d. Exploratory Endpoints to Refine Study Intervention Design, Implementation, and Scalability

4.d.1. Caregiver/Dyad CBT Feasibility Data. We will collect these data for use in future studies based on prior work exploring couples-based CBT in breast cancer patients with BID⁶⁷.

4.d.2. Qualitative Assessment of Experience with BID and CBT. To better understand patient experiences with BID not captured in the questionnaires as well as their experiences with CBT, we will perform semi-structured interviews. Participants will be asked to 1) discuss their preferences about the timing, format and content of the CBT sessions 2) describe their program experiences and offer recommendations to improve delivery, and 3) and assess feasibility and acceptability of the intervention. This mixed methods approach will allow for an in-depth exploration of patient experiences⁶⁸, help refine the study intervention, and inform intervention implementation for future studies⁶⁹.

5.0 Inclusion and Exclusion Criteria/ Study Population

5.a. Study Participants. The study population is adult patients with head and neck cancer undergoing surgery at MUSC with body image disturbance post-treatment.

5.b. Screening for Eligibility. The study team member in collaboration with the electronic medical record and otolaryngology head and neck cancer clinical team, will identify patients ages 18 or older with a pathologic diagnosis of squamous cell carcinoma of the upper aerodigestive tract (oral cavity, oropharynx, hypopharynx, or larynx) or skin of the head and neck presenting for consultation. These patients will be potentially eligible for the study. They will complete a screening BIS questionnaire 1 month after completion of treatment; those with scores ≥ 5 will be eligible for the study. Those with scores < 5 will not be eligible for the study, their BIS questionnaire will be shredded, and no personal information about the patient will be saved. The individual data elements from the clinical records that will be accessed in order to identify potential participants for recruitment include:

1. Name
2. Date of birth, to confirm that potential participant is 18 years or age or older
3. Diagnosis of squamous cell carcinoma of the upper aerodigestive tract or skin of the head and neck.

5.c. Inclusion/Exclusion Criteria:

5.c.1. Inclusion Criteria:

- Pathologic diagnosis of squamous cell carcinoma of the upper aerodigestive tract (oral cavity, oropharynx, hypopharynx, larynx) or cutaneous malignancy of the head and neck (e.g. squamous cell, basal cell, melanoma, etc)
- Age ≥ 18
- American Joint Committee on Cancer (AJCC) stages I-IV
- Curative intent therapy with surgery with or without adjuvant therapy
- BIS score ≥ 5 at 1 month post-treatment

5.c.2. Exclusion criteria:

- Inability to speak English
- Known distant metastatic disease
- Inability or unwillingness of subject or legal guardian/representative to give informed consent

5.d. Inclusion of Women and Minorities. Men and women and members of all races and ethnic groups are eligible for this study.

5.e. Subgroup Distribution: To ensure a reasonable distribution of patients based on potentially relevant characteristics, we will recruit patients diverse by age, race, gender, cancer site, and type of reconstruction.

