We will call potential participants who have agreed to be contacted about research in EPIC, to discuss the study. For those who have not agreed to be contacted about research in EPIC, we will mail a study recruitment letter prior to their planned clinic visit. If a patient is interested in participating, the coordinator will schedule an in-person meeting to complete screening BIS questionnaire; those with scores ≥ 5 will be eligible for the study. Eligible patients after screening who are still interested in enrolling will complete informed consent paperwork in the clinic using protocols from our previous research. The study participants may include patient's of the PI's, but will not be exclusively patient's of the PIs. For potential participants where the PI is not the attending physician and the potential participant has not consented to participate in research per EPIC, then the attending physician for the patient will introduce the study idea to the potential participant. Other than the notification of the study by the attending physician for potential trial participants, the research team will not ask other clinicians to be involved in recruitment. All of the recruitment will be handled by the study coordinator and team.

8.c. Recruitment Materials. A study recruitment letter will be mailed to potential study participants prior to face-face enrollment and informed consent. A copy of the study recruitment letter has been uploaded into eIRB.

8.d. Participant Compensation. Compensation via checks will be provided to participants for the (n=20 participants). The checks will compensate subjects for time, travel, and enrollment. Participants will receive \$20 for enrollment and \$20 for completion of the study ($\$20 + \$20 = \$40/\text{patient} \times 20 \text{ patients} = \800).

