9.0 Consent Process

Informed consent will be obtained for the study. Those who are interested in enrolling in the study will complete a screening BIS questionnaire. A waiver of written informed consent will be obtained to allow patients to complete the screening BIS questionnaire. Those with scores < 5 will not be eligible for the study, their BIS questionnaire will be shredded, and no personal information about the patient will be saved. Those with $BIS \geq 5$ will be eligible for the study. For those subjects who are eligible and interested in enrolling, we will describe the elements of the informed consent and HIPAA forms and answer any questions. Subjects will have time to read the informed consent and HIPAA documents on their own. Any additional questions will be answered and then patients will be asked to sign informed consent and HIPAA forms. All participants will receive a copy of their informed consent and HIPAA forms for their records. Separate copies of the documents will be stored in the study binder under each patient's section. Copies of these documents have been uploaded into eIRB.

9.a. Method of Obtaining Consent. Informed consent will occur via face-face discussion between one of the study team members designated to perform informed consent and the potential study participant. The PI, co-investigators, collaborators, and study coordinator will be authorized to obtain informed consent.

9.b. Location of Informed Consent Process. The informed consent process will take place in a private room in the 10th floor Rutledge Tower Head and Neck Cancer Clinic or in Hollings Cancer Center

9.c. Consenting Parties. Only the study participant will provide informed consent. If the participant is not able to consent, the legally authorized representative [LAR] will provide informed consent (and appropriate documentation to substantiate the LAR will be uploaded or verified in EPIC).

9.d. Waiting Period for Informed Consent. Subjects will be allowed up to one month to decide whether or not to participate in the study.

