10.b.2. CBT Intervention and Implementation. At the 1-month post-HNC treatment time point, patients with BID as determined by BIS score ≥ 5 will undergo time-limited CBT consisting of 5 weekly sessions. Each session will be guided by the HNC BID module that we develop, but customized to each patient's specific concerns⁴⁰. Each session will last ~60 minutes and be conducted one-one with [name], who will administer the CBT as part of clinical psycho-oncology care at HCC. Patients will complete questionnaires prior to CBT and 1 and 3 months after CBT (**Figure 3**). We considered alternate dose schedules of CBT but chose a 5-week schedule because evidence suggests that brief (e.g. 5-week) CBT reduces anxiety and depression and improves QOL in cancer patients⁵⁸. To overcome the expected travel distance-related barrier to receipt of CBT, we will offer the option of home-based, telemedicine CBT through an existing MUSC program⁵⁹. This will consist of one CBT session at HCC followed by iPad-based, tele-CBT for the next 4 sessions. Patients will receive the iPad and brief training session from MUSC Center for Telehealth staff at the in-person CBT session. They will take the iPads home, use them for the next 4 tele-CBT sessions, and mail them back to MUSC at the study conclusion.

10.b.3. Standardization and Treatment Fidelity. Standardization of intervention administration is critical for study validity and reproducibility. All CBT will be delivered by one psycho-oncologist (SM) with standardized content (regardless of whether the modality is in-person or tele-health CBT). To ensure fidelity of the intervention, the study psycho-oncologist will keep an intervention tracking log which captures data fields such as patient attendance at the session, CBT content delivered, completion of patient homework, technical problems with the session, rating of session length, patient engagement, and patient comprehension (to be completed by psycho-oncologist), and session duration,

10.c. Study Variables

10.c.1 Antecedent Variables.

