11.0 Data Management

11.a. Data Analysis Plan for Primary Endpoint. The primary endpoint is BIS scores measured at specific time points (Figure 3). We will summarize BIS at each time point by estimating mean and corresponding 95% confidence intervals (CIs), median, standard deviation (SD), inter-quartile range, and range. We will also construct boxplots and spaghetti plots of serially collected BIS scores to provide visual assessment of temporal changes in BIS. Finally, we will analyze BIS scores over time using linear mixed effects (LME) regression models with time as a fixed effect (considered as categorical variable) and subject-specific random effects to account for the correlation among measures obtained from the same subject over time. We will consider transformations for BIS scores to induce approximate normality and stabilize variance. BIS comparisons over time will be conducted using model-based linear contrasts. We will also consider Wilcoxon sign rank tests to compare BIS scores if variable transformations of BIS fail to induce approximate normality. We will not be specifically controlling for telemedicine vs face-to-face CBT but have planned subset analyses to see if differences exist based on method of CBT delivery.

11.b. Power Analysis/Sample Size Justification. Power analyses were performed using PASS 2008, version 08.0.13. Based on our preliminary data, we expect 35 patients/year to be eligible for the study, of

whom 84.6% will be 'somewhat likely' or 'highly likely' to participate in an intervention for their BID (unpublished data). Assuming that we enroll two-thirds of the eligible and 'likely to participate' subjects, if we enroll over 12 months, we would achieve our sample size of $n=20$.

The study seeks to characterize the effects of CBT on BID. **Figure 4** shows the power to detect absolute differences in BIS for $n=20$ based on a paired t-test with SD (BIS difference) = 3.8 (preliminary data), and two-sided $\alpha = 0.05$. We estimate power to be at least 80% to detect a difference in BIS scores of

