approximately 2.5 or greater, a power estimate that is conservative given our proposed analysis plan using LME regression that borrows strength over time. In our preliminary data, we observed BIS differences of approximately 2 points before and after surgery without any intervention. We expect even larger changes in BIS based on the CBT intervention, which is reasonable to provide preliminary evidence of CBT efficacy for our sample of $n=20$.

11.c Data Analysis Plans for Secondary Endpoints.

Sociodemographic and oncologic variables will be summarized using descriptive statistics, including mean, median, standard deviation, interquartile range, and range for continuous variables, and frequencies and percentages for categorical variables.

Additional study variables, including: **shame and stigma scale score** (summed score ranging from 0 to 80); PROMIS measures of **depression, anxiety, social roles, and isolation** (summed scores each ranging from 0 to 16); and **head and neck performance status** (summed score ranging from 0 to 100), will be summarized using descriptive statistics. Additionally, we will evaluate the association between each of these study variables and response to CBT. Specifically, we will examine the association between change in BIS ($\Delta\text{BIS}_1 = 1$ month post-CBT versus baseline; and $\Delta\text{BIS}_3 = 3$ month post-CBT versus baseline) and each variable using Spearman's correlation coefficient.

Response variables (in addition to **Figure 4: Power to detect change in BIS for a sample size of 20 based on a paired t-test with two-sided $\alpha = 0.05$ [SD(BIS difference) = 3.8].** (summed score ranging from 0 to 80); **body image coping** (summed score ranging from 35 to 140). De... and neck cancer QoL (summed score ranging from 35 to 140). De... summarize each variable at each time point. We will also examine the association between change in BIS and each variable using Spearman's correlation coefficient. Finally, we will evaluate the effect of CBT on each response variable using the LME regression model approach described in Section 11.a.

CBT utilization patterns and **caregiver/dyad CBT feasibility data** will be summarized using descriptive statistics.

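### Is the baseline of the BIS comparison the screening score that was selected at 5 or above?

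*Protocol*

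**What the plan says.** Eligibility rests on a BIS of at least 5 one month after treatment (section 5.b: "They will complete a screening BIS questionnaire 1 month after completion of treatment; those with scores ≥ 5 will be eligible"). BIS is also the primary outcome (sections 4.a.1 and 10.c.2.a.1).

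Consent comes after screening (section 8.b: "Eligible patients after screening who are still interested in enrolling will complete informed consent paperwork in the clinic"). Section 9.0 obtains a waiver of written consent for the screening form alone. Section 9.d adds: "Subjects will be allowed up to one month to decide whether or not to participate in the study".

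On treatment and assessment, section 10.b.2 states "At the 1-month post-HNC treatment time point, patients with BID as determined by BIS score ≥ 5 will undergo time-limited CBT" and then "Patients will complete questionnaires prior to CBT and 1 and 3 months after CBT". Section 1.0 has the body image measures "Reliable, validated PRO measures of BID will be collected before, 1 month and 3 months after the CBT intervention".

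Section 11.a models BIS over time with time as a categorical effect. Section 11.c forms change scores at each "month post-CBT versus baseline". Sections 10.b.2, 10.d.1 and 11.a all refer to Figure 3 for the time points. That figure is not in the text available here.

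**The concern.** A trial that selects patients for a high score on a noisy scale, and then measures change from that same score, will on average see a fall even if treatment does nothing. There is no control arm to subtract it.

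The visible text leaves room for this. No sentence says that BIS is completed again after consent, and none defines the baseline of section 11.c. The protocol says what happens to forms scoring below 5 (they are destroyed) but not whether forms scoring 5 or more enter the analysis. Read literally, section 10.b.2 puts the BIS determination and CBT at the same one-month point, so one form could serve both purposes. Section 9.d, by contrast, could delay CBT by up to a month after screening.

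At stake is the size of the change passed on to the randomised trial that section 15.b foresees. The pilot has no stated go/no-go rule.

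**Working it through.** **1. The plan's own figure.** Inputs from sections 11.a and 11.b: n = 20, SD of the BIS difference 3.8, paired t-test, two-sided alpha 0.05, difference 2.5. The noncentrality is 2.5/(3.8/√20) = 2.94 on 19 degrees of freedom. Power is 79.7%, and exactly 80% is reached at 2.51 points. The stated figure is sound and does not depend on which form is the baseline.

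**2. The artefact if the screening score were the baseline.** Assumptions: normal scores, no treatment effect, total BIS SD of 4 to 7 (not given in the protocol), and either all or half of the variance of the difference being noise.

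- Error variance per score: v = share × 3.8²/2, which is 7.22 (all) or 3.61 (half).
- Expected fall = (v/SD) × φ(z)/p, where p is the proportion at or above the cut-off and z = Φ⁻¹(1 − p).
- The table in section 2.i has 14 of 28 patients with BIS of 5 or more, so p = 0.50, z = 0 and φ(z)/p = 0.798.
- Section 2.i also reports body image disturbance in 85.7% of these 28 patients, with no cut-off stated. As a sensitivity value, p = 24/28 gives φ(z)/p = 0.263.

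| p | Noise share | SD 4 | SD 5 | SD 6 | SD 7 |
|---|---|---|---|---|---|
| 0.50 | all | 1.44 | 1.15 | 0.96 | 0.82 |
| 0.50 | half | 0.72 | 0.58 | 0.48 | 0.41 |
| 0.857 | all | 0.48 | 0.38 | 0.32 | 0.27 |
| 0.857 | half | 0.24 | 0.19 | 0.16 | 0.14 |

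Against 2.5 points, the extremes are 0.14/2.5 = 6% and 1.44/2.5 = 58%. Simulated rejection rates with no effect (n = 20, paired t-test, nominal 5%) are 7–41% at p = 0.50 and 5–9% at p = 0.857.

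**3. The artefact if a separate pre-CBT score is the baseline.** With independent errors on the two forms, the expected fall is 0.00 and the rejection rate stays at 5%. If the forms are completed close together and their errors correlate at 0.5 (assumed), half of the artefact remains. With all noise, that is 0.72 to 0.41 at p = 0.50 and 0.24 to 0.14 at p = 0.857, for SD 4 to 7.

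**4. Which case the text describes.** Sections 5.b, 8.b and 9.0 consistently call the pre-consent form a screening questionnaire, and the waiver covers that form only. Sections 1.0 and 10.b.2 separately have study measures completed before CBT. Section 1.0 says these are measures of body image disturbance, and BIS is the protocol's instrument for that. Two administrations is the natural reading. No sentence carries the screening score forward.

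**5. The timings.** The month in section 9.d is a maximum with no stated start. Section 8.b has patients phoned or sent a letter before the screening visit, so some or all of it may come before screening. In section 10.b.2, the one-month point can attach to the BIS determination, as it does in the inclusion criteria. Five weekly sessions cannot all fall at one time point in any case. Follow-up is set at 1 and 3 months after CBT, so a later start moves the whole sequence and leaves the contrasts as defined.

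**The case for a change.** The strongest reply is that conduct cannot be repaired afterwards. If no second BIS is collected before the first session, no analysis plan can recover it, and stating the point would take a few sentences and at most one 10-item form. Even two administrations would not by themselves say which score is the baseline, or whether the screening score enters the mixed model.

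Part of this stands. The term is undefined in the visible text, and where screening and the first session fall close together a single form could be used twice. But the protocol does have a place for the schedule, Figure 3, and its absence here comes from how the text was extracted. Which record counts as baseline is also commonly settled in a statistical analysis plan, and an analyst would ordinarily take the last value before treatment.

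The size of the harm is also weakly supported. The protocol gives no BIS mean, SD or reliability. The 3.8 appears to come from differences before and after surgery, which can include real variation in change, so treating all of it as noise is an upper bound. With half the scores above 5 and an SD of 4 to 7, the normal model places 11–24% of scores below zero, which the scale does not allow. The 85.7% cannot be the share at or above 5 in patients of whom 14 of 28 reached that cut-off; leaving it out raises the lower end to 0.4 points.

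**Conclusion.** The concern does not call for a change. It identifies an undefined term whose harm depends on one reading, that the screening form is reused as baseline, and the visible wording leans against that reading. On the natural reading, the artefact is zero with independent errors and about half the tabulated size at an assumed error correlation of 0.5. If the screening score were reused, the artefact would be roughly 0.1 to 1.4 points under the assumptions shown, a range too wide to be an estimate.

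Sections 5.b, 8.b, 9.d and 10.b.2 are in mild tension on the timing of screening, consent and CBT, and they could be reconciled when the text is next edited. Which timing is intended is for the sponsor to say, and the definition of the contrasts does not depend on it. Untreated change during CBT and follow-up stays uncontrolled under either baseline. That is a property of the single-arm pilot design, which section 10.a states openly, and section 15.b presents the results as preliminary data for a randomised trial.
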